# SCHEDULE OF EVENTS (SUBSEQUENT TO WEEK 10)

	Treatment Week									
	Week 13 Day 1 (± 3 days)	Week 16 Day 1 (± 3 days)	Week 19 Day 1 (± 3 days)	Every 3 Weeks after Week 19 Day 1 (± 3 days)	Approx. every 9 Weeks after Week 19 Day 1 (± 1 week)	Week 46 Day 1 (± 1 week)	End of Study  Follow-Up			
Physical Exam  and Vital Signs 	X	X	X	X	X	X	X			
Performance Status (ECOG)	X	X	X		X	X	X			
Adverse Events 	X	X	X	X	X	X	X			
Concomitant Medications 	X	X	X	X	X	X	X			
CBC (w/diff, platelet count) 5	X	X	X		X	X	X			
Serum Chemistry 	X	X	X		X	X	X			
Thyroid Function Tests and CEA/TA4 	X		X	X			X			
Urinalysis 							X			
Coagulation Assessment 							X			
Pregnancy Test 							X			
Research Blood Collection 11		X	$(X + 3 \text{ wk})^{11}$			$(X + 3 \text{ wk})^{11}$	X			
GX-188E Vaccination (i.m.)	X		X			$(X)^{16}$				
Pain Assessment 	X		X			X				
Pembrolizumab (i.v.) 	X	X	X	X		X				
Tumor Biopsy  (optional)							X			
Radiographic Evaluation of Tumor Burden 			X		X		X			

- 1. Screening and End of Study require a complete physical exam. For all other study, physical exams should be symptom-directed and clinically significant findings reported as adverse events.
- 2. Vitals to include heart rate, respiratory rate, temperature, blood pressure (systolic and diastolic) weight, and height. Height only needs to be obtained at screening.
- 3. Adverse event monitoring begins once a patient receives the first dose of either agent of the investigational study regimen and continues until 28 days after the last administration of study treatment, or until the initiation of a new anti-cancer therapy, whichever occurs first. For Serious Adverse Events (SAEs), follow up will continue for 90 days.
- 4. Concomitant medication is defined as any prescription or over-the-counter preparation, including vitamins and supplements. All concomitant medications from 28 days before Day 1 through the end of the subject's study participation must be recorded. (During the follow-up period after the end of the clinical trial, only the data about the antineoplastic therapy (surgical therapy, chemotherapy, radiation therapy, etc.) treated after the end of the subject's study participation is recorded.)
- 5. CBC w/differential to include: Hemoglobin, Platelets, Red Blood Cells, White Blood Cells, Basophils (%), Eosinophils (%), Lymphocytes (%), Monocytes (%), Neutrophils (Abs) and Hematocrit.
- 6. At all timepoints, (except for Screening), only a basic metabolic panel (Na, K, CO2 or bicarbonate, Cl, Ca, BUN, creatinine & glucose) plus AST and ALT are required. Other tests may be ordered as clinically indicated.
- 7. Includes thyroid-stimulating hormone (TSH), free thyroxine (FT4), and T3. Thyroid function tests and CEA/TA4 levels will be evaluated approximately every 6 weeks for the duration of study participation (i.e., Screening/Baseline, Week 7, Week 13, Week 19, Week 25, etc).
- 8. Urinalysis is only required at Screening, Week 1 Day 1, Week 10 Day 1, and End of Study. Urinalysis should be ordered as clinically indicated at any other timpoint.
- 9. Coagulation assessment includes: prothrombin time, partial thromboplastin time, and international normalized ratio (PT/PTT/INR). Coagulation assessments are only required at Screening and End of Study. On-treatment coagulation assessments (e.g., Week 10) are only required if a biopsy is planned and must be evaluated within 24 hours prior to biopsy collection on the same day.
- 10. All females of child-bearing potential must have serum or urine pregnancy test at End of Study.
- 11. Blood collection.Samples will include serum for immune response Flt-3L(Screening, Week10, Week22, Week49 then after every 27 weeks) and whole blood for PBMC T cell responses(Screening, Week1, Week4, Week7, Week10, Week16, Week22, Week49 then after every 27 weeks). Samples obtained at all time points associated with study treatment administration, except for Screening, should be obtained prior to administration of either/both agents.
- 12. Pain assessment using a 0-10 numeric pain rating scale will be administered prior to and 5 minutes (± 2 minutes) following each GX-188E electroporation procedure
- 13. Pembrolizumab will be administered every 3 weeks for the duration of study participation
- 14. Patients with biopsy-accessible lesions will be asked to provide an optional biopsy sample at approximately Week 10 (or End of Study if the patient discontinues prior to Week 10) for paired biopsy analysis. Biopsies will be evaluated for bio-markers using immunohistochemistry but not limited to it.
- 15. Radiographic evaluations of tumor burden by RECIST v1.1 will be performed by a blinded independent central reviewer approximately every 9 weeks, or more frequently as clinically indicated, and at End of Study if the reason for discontinuation is other than for confirmed radiologic disease progression. Confirmatory scans are required approximately 4 weeks after any scan that indicates either an objective response, stable disease or disease progression.
- 16. An optional GX-188E administration may be given at week 46 if it is in the best interests of the patient, as determined by the investigator, once the patient has completed 37 weeks of treatment. Additional GX-188E administration(s) may be given to the subject after discussion with the sponsor.
- 17. The End of Study (EOS) visit must occur within 28 days of treatment discontinuation/completion (Week 103 Day 1) and prior to initiation of any new anti-cancer thepapy/regimen.

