# 12.2.1 Dose Modification and Toxicity Management for Immune-related AEs Associated with Pembrolizumab

AEs associated with pembrolizumab exposure may represent an immune-related response. These irAEs may occur shortly after the first dose or several months after the last dose of pembrolizumab treatment and may affect more than one body system simultaneously. Therefore, early recognition and initiation of treatment is critical to reduce complications. Based on existing clinical study data, most irAEs were reversible and could be managed with interruptions of pembrolizumab, administration of corticosteroids and/or other supportive care. For suspected irAEs, ensure adequate evaluation to confirm etiology or exclude other causes. Additional procedures or tests such as bronchoscopy, endoscopy, skin biopsy may be included as part of the evaluation. Dose modification and toxicity management guidelines for irAEs associated with pembrolizumab are provided in Table 4.

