# Table 4. Dose Modification and Toxicity Management Guidelines for Immune-related AEs Associated with Pembrolizumab.

#### General instructions:

- 1. For Severe and life-threatening irAEs, should be treated with IV corticosteroid should be initiated first corticosteroids followed by oral steroidsteroids. Other immunosuppressive treatment should be initiated begin if the irAEs cannot beare not controlled by corticosteroids.
- 2. Pembrolizumab must be permanently discontinued if the irAE does not resolve or the corticosteroid dose is not ≤10 mg/day within 12 weeks of the last pembrolizumab treatment.
- 3. The corticosteroid taper should begin when the irAE is  $\leq$  Grade 1 and continue at least 4 weeks.
- 4. If pembrolizumab has been withheld, pembrolizumab may resume after the irAE decreased to ≤ Grade 1 after corticosteroid taper.

	Toxicity grade (CTCAE v4.0 or			
	the most recent	Action with	Corticosteroid and/or	
irAEs	version)	pembrolizumab	other therapies	Monitor and follow-up
Pneumonitis	Recurrent Grade 2, Grade 3 or 4	Permanently discontinue	
 
Administer         corticosteroids         (initial dose of 1-2         mg/kg prednisone         or equivalent)         followed by taper
 
Add prophylactic         antibiotics for         opportunistic         infections
 
	
 
Monitor participants for signs and symptoms of pneumonitis
 
Evaluate participants with suspected pneumonitis with radiographic imaging and initiate corticosteroid treatment
 

Diarrhea / Colitis	Grade 2 or 3	Withhold	Administer     corticosteroids     (initial dose of 1-2     mg/kg prednisone     or equivalent)     followed by taper	Monitor participants for signs and symptoms of enterocolitis (ie, diarrhea, abdominal pain, blood or mucus in stool with or without fever) and of bowel
	Recurrent Grade 3 or Grade 4	Permanently discontinue		perforation (ie, peritoneal signs and ileus).  Participants with ≥ Grade 2 diarrhea suspecting colitis should consider GI consultation and performing endoscopy to rule out colitis.  Participants with diarrhea/colitis should be advised to drink liberal quantities of clear fluids. If sufficient oral fluid intake is not feasible, fluid and electrolytes should be substituted via IV infusion.
AST or ALT elevation or Increased Bilirubin	Grade 2 ª	Withhold	Administer corticosteroids (initial dose of 0.5- 1 mg/kg	Monitor with liver function tests (consider weekly or more frequently until liver

	1		I 1:	

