			prednisone or equivalent) followed by taper	enzyme value returned to baseline or is stable
	Grade 3 b or 4 c	Permanently discontinue	Administer     corticosteroids     (initial dose of 1-2     mg/kg prednisone     or equivalent)     followed by taper	
Type 1 diabetes mellitus (T1DM) or Hyperglycemia	New onset T1DM or Grade 3 or 4 hyperglycemia associated with evidence of β-cell failure	Withhold d	Initiate insulin replacement therapy for participants with T1DM     Administer antihyperglycemic in participants with hyperglycemia	Monitor participants for hyperglycemia or other signs and symptoms of diabetes.
Hypophysitis	Grade 2 Grade 3 or 4	Withhold or permanently discontinue d	Administer     corticosteroids     and initiate     hormonal     replacements as     clinically	Monitor for signs and symptoms of hypophysitis (including hypopituitarism and adrenal insufficiency)
Hyperthyroidism	Grade 2	Continue	
 
indicated.
 
Treat with non-selective betablockers (eg, propranolol) or thionamides as appropriate
 
	
 
Monitor for signs and symptoms of thyroid disorders.
 

	Grade 3 or 4	Withhold or permanently discontinue d		
Hypothyroidism	Grade 2, 3, 4	Continue	Initiate thyroid replacement hormones (eg, levothyroxine or liothyroinine) per standard of care	Monitor for signs and symptoms of thyroid disorders.
Nephritis: grading according to increased creatinine or acute kidney injury	Grade 2 Grade 3 or 4	Withhold  Permanently discontinue	Administer     corticosteroids     (prednisone 1-2     mg/kg or     equivalent)	Monitor changes of renal function
Myocarditis	Grade 1	Withhold	Based on severity of AE administer corticosteroids	Ensure adequate evaluation to confirm etiology and/or exclude other causes
	Grade 2, 3 or 4	Permanently discontinue		
All Other immune- related AEs	Persistent Grade 2 Grade 3	Withhold or discontinue based on the	Based on severity of AE administer corticosteroids	Ensure adequate evaluation to confirm etiology or exclude other causes
	Grade 4 or recurrent Grade 3	type of event e Permanently discontinue		

- a. AST/ALT: >3.0 5.0 x ULN if baseline normal; >3.0 5.0 x baseline, if baseline abnormal; bilirubin:>1.5 3.0 x ULN if baseline normal; >1.5 3.0 x baseline if baseline abnormal
- b. AST/ALT: >5.0 to 20.0 x ULN, if baseline normal; >5.0 20.0 x baseline, if baseline abnormal; bilirubin:>3.0 10.0 x ULN if baseline normal; >3.0 10.0 x baseline if baseline abnormal

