- c. AST/ALT: >20.0 x ULN, if baseline normal; >20.0 x baseline, if baseline abnormal; bilirubin: >10.0 x ULN if baseline normal; >10.0 x baseline if baseline abnormal
- d. The decision to withhold or permanently discontinue pembrolizumab is at the discretion of the investigator or treating physician. If control achieved or ≤ Grade 2, pembrolizumab may be resumed.
- e. Events that require discontinuation include but are not limited to: Guillain-Barre Syndrome, encephalitis, Stevens-Johnson Syndrome and toxic epidermal necrolysis.

Requirements for treatment discontinuation are not strict and individual situations will be evaluated on a case-by-case basis. Treatment discontinuation for both non-hematological and hematological toxicities will be based on the Principal Investigator's judgment following discussion with the Sponsor's Medical Monitor.

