# 12.2.4 Supportive Care Guidelines for Events of Clinical Interest and Immunerelated Adverse Events (irAEs)

Events of clinical interest of a potential immunologic etiology (irECIs) may be defined as an adverse event of unknown etiology, associated with drug exposure and is consistent with an immune phenomenon. irAEs may be predicted based on the nature of the pembrolizumab compound, its mechanism of action, and reported experience with immunotherapies that have a similar mechanism of action. Special attention should be paid to AEs that may be suggestive of potential irAEs. An irAE can occur shortly after the first dose or several months after the last dose of treatment.

If an irAE is suspected, efforts should be made to rule out neoplastic, infectious, metabolic, toxin or other etiologic causes prior to labeling an adverse event as an irAE. Patients who develop a Grade 2 or higher irAE should be discussed immediately with the Sponsor.

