- 8. Serum Chemistry at Screening to include: Sodium, Potassium, CO2 or bicarbonate, Chloride, Albumin, Alkaline Phosphatase, ALT, AST, Total Bilirubin, Blood Urea Nitrogen, Calcium, Creatinine, Glucose, Magnesium, Phosporus, Total Protein, LDH, and Cockcroft-Gault calculated Creatinine Clearance. At all other time points, only a basic metabolic panel (Na, K, CO2 or bicarbonate, Cl, Ca, BUN, creatinine & glucose) plus AST and ALT are required. Other tests may be ordered as clinically indicated. However, if subjects had the result of serum chemistry tests at the screening which met the all in/exclusion criteria and the investigators judged that the result of same tests at W1D1 were no clinical significance, they can be enrolled.
- 9. Serology at Screening to include: HIV Ag/Ab, HAV Ab (IgM), HBV Ab, HBV sAg, HCV Ab, HCV RNA (HCV real time PCR)
- 10. Includes thyroid-stimulating hormone (TSH), free thyroxine (FT4), and T3. Thyroid function tests and CEA/TA4 levels will be performed approximately every 6 weeks.
- 11. Urinalysis is only required at Screening, Week 1 Day 1, Week 10 Day 1, and End of Study. Urinalysis should be ordered as clinically indicated at any other timpoint.
- 12. Coagulation assessment includes: prothrombin time, partial thromboplastin time, and international normalized ratio (PT/PTT/INR). Coagulation assessments are only required at Screening and End of Study. On-treatment coagulation assessments (e.g., Week 10) are only required if a biopsy is planned and must be evaluated within 24 hours prior to biopsy collection on the same day.
- 13. All females of child-bearing potential must have a negative serum or urine pregnancy test within 3 days prior to the first dose of study treatment.
- 14. Blood collection. Samples will include serum for immune response Flt-3L(Screening, Week10, Week22, Week49 then after every 27 weeks) and whole blood for PBMC T cell responses(Screening, Week1, Week4, Week7, Week10, Week16, Week22, Week49 then after every 27 weeks). Samples obtained at all time points associated with study treatment administration, except for Screening, should be obtained prior to administration of either/both agents. Blood sample for Flt-3L will be collected at screening visit, week 10, week 22, week 49 and every 27 weeks thereafter.
- 15. Pain assessment using a 0-10 numeric pain rating scale will be administered prior to and 5 minutes (± 2 minutes) following each GX-188E electroporation procedure

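### After Screening no scheduled serum total bilirubin or alkaline phosphatase is required, which leaves two narrow gaps in liver monitoring that are cheap to close (minor)

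*Protocol*

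**What the plan says.** Protocol Appendix 1 sets the chemistry in two footnotes. In the Screening-to-Week 10 schedule, footnote 8 asks for a full panel at Screening, including total bilirubin and ALP. For other visits its list ends "creatinine & glucose) plus AST and ALT are required". In the schedule after Week 10, footnote 6 reads "At all timepoints, (except for Screening), only a basic metabolic panel", again with AST and ALT added. End of Study falls under the same limit. Both footnotes leave further tests to clinical judgement.

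Section 20.1.3 speaks of a comprehensive chemistry panel but refers to the Schedule of Events for what is done. Appendix 4 lists bilirubin and ALP but sets no on-treatment visits.

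Two safety rules use these analytes:

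- **Table 4 (Section 12.2.1), liver row.** Raised bilirubin counts on its own as an alternative to raised enzymes. Grade 2 means withhold pembrolizumab, and Grade 3 or 4 means stop permanently. Bilirubin Grade 2 begins above 1.5 times ULN when baseline is normal. AST/ALT is graded against the patient's own value when that was raised; the Grade 2 band then ends at "5.0 x baseline, if baseline abnormal". The text after the table adds "Requirements for treatment discontinuation are not strict and individual situations will be evaluated on a case-by-case basis".
- **Section 20.8, liver ECI.** This needs AST or ALT of at least 3 times ULN, total bilirubin of at least 2 times ULN and ALP below 2 times ULN together. It must reach the sponsor within 24 hours.

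Table 1 (Section 10.7.1) admits AST/ALT up to 2.5 times ULN, or up to 5 times ULN with liver metastases.

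**The concern.** The protocol acts on serum bilirubin in one rule and on bilirubin plus ALP in another, but schedules neither after Screening. What prompts a site to measure them is the scheduled AST/ALT. That prompt fails in two situations: when bilirubin rises and the enzymes do not, and when the enzymes were already high at entry. In either case, a liver event could be recognised later than the blood already being drawn would allow.

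**Working it through.** The protocol states no figure to reproduce here. The check sets the schedule beside the two rules and counts visits.

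**Required chemistry draws after the first dose, for a patient treated to Week 103**

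- Weeks 2, 3, 4, 7, 10, 13, 16, 19: 8 draws.
- Every 9 weeks after Week 19, at Weeks 28, 37, 46, 55, 64, 73, 82, 91, 100: 9 draws (Week 46 counted once).
- End of Study: 1 draw.
- Total: 8 + 9 + 1 = 18, of which 0 require total bilirubin or ALP.

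Week 1 Day 1 is left out because it precedes dosing and Section 16.2 lets recent Screening results stand in for it.

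**Pembrolizumab visits after Week 19**

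Weeks 22 to 103 every 3 weeks: (103 − 22)/3 + 1 = 28 visits. Required chemistry falls at 9 of them. At the other 28 − 9 = 19, Section 16.11.1 leaves laboratory work to clinical need and local practice, which may include liver tests.

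**Gap 1: bilirubin without enzymes**

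Table 4 would withhold treatment above 1.5 times ULN from a normal baseline. The number of scheduled serum measurements that could show this after Screening is zero.

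**Gap 2: enzymes high at entry**

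With an abnormal baseline, Table 4 Grade 2 starts above 3.0 × baseline. The ECI enzyme component stays at 3 times ULN.

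| AST/ALT at entry | Table 4 Grade 2 starts above | ECI enzyme component |
|---|---|---|
| Normal | 3 × ULN | Newly reached at 3 × ULN on a scheduled test |
| 2.5 × ULN (ceiling without liver metastases) | 3 × 2.5 = 7.5 × ULN | Newly reached at 3 × ULN on a scheduled test |
| 3 × ULN (liver metastases) | 3 × 3 = 9 × ULN | Already met at entry |
| 5 × ULN (liver metastases) | 3 × 5 = 15 × ULN | Already met at entry |

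In the last two rows the enzyme component is already met, so the ECI turns on bilirubin and ALP. Scheduled AST/ALT gives no Table 4 prompt to measure them until the enzymes have tripled from baseline. In the first two rows, a scheduled result crossing the ECI's own enzyme threshold is visible, even where Table 4 grades it later.

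**The case against.** The strongest reply is that AST/ALT as a scheduled sentinel, with further tests when it rises, is a legitimate design, and that the protocol supports it in many places:

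- The Table 4 liver row says "Monitor with liver function tests (consider weekly or more frequently until liver" enzymes settle.
- For suspected immune-related events, Section 12.2.1 tells sites to "ensure adequate evaluation to confirm etiology or exclude other causes".
- Section 12.2.4 adds "Patients who develop a Grade 2 or higher irAE should be discussed immediately with the Sponsor".
- Section 20.1 lets investigators evaluate safety more often than required.
- Section 20.8 accepts unscheduled results, mentions site guidance that is not in these documents, and allows further work-up of abnormal liver tests short of the ECI after consultation with the sponsor.
- Appendix 4 urinalysis includes bilirubin, and the schedule says "Urinalysis is only required at Screening, Week 1 Day 1, Week 10 Day 1, and End of Study". After dosing that means Week 10 and End of Study.
- Symptom-directed examinations take place at each visit.
- Bilirubin and ALP are known from Screening, so an investigator can see which patients enter close to the ECI.

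Most of this stands. For patients entering below 3 times ULN, the sentinel gives reasonable cover for enzyme-led events. But all of it is discretionary or indirect. The Table 4 advice does not define its panel and leaves frequency to be considered. Urine bilirubin does not supply the serum values that Table 4 and the ECI use. No text requires serum bilirubin or ALP, even when AST/ALT is raised.

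Three stronger readings are tempting, and the documents do not support them. First, a reader might infer that the ECI cannot be ascertained; unscheduled tests count, so this is a gap in required monitoring and not a bar to detection. Second, a reader might infer that every patient with raised entry enzymes lacks a prompt; that holds only for entry at 3 times ULN or more. Third, a reader might see a contradiction with Section 20.1.3; that section defers to the schedule.

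**Conclusion.** The point holds as a minor, inexpensive improvement to safety monitoring. None of up to 18 required draws after the first dose includes serum total bilirubin or ALP. The consequences are confined to bilirubin-led rises in any patient, and to the ECI in patients with liver metastases entering at 3 to 5 times ULN.

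The conclusion assumes that a site runs only the required panel; the documents do not show how often that happens. They also give no count of patients entering at 3 to 5 times ULN and no frequency for isolated bilirubin rises, so the number affected is unknown and may be very small. Because V4.0 records that Part B had passed its first stage, only patients still on treatment or yet to enrol would benefit.

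ORR24 is unaffected. Under SAP Section 6.3 unscheduled values stay out of by-visit summaries but count towards worst-case values, so recorded discretionary bilirubin results can still be read beside the ECI table in SAP Section 16.1.8.

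**What to change.** Add total bilirubin and ALP to the required post-Screening chemistry in footnote 8 (Screening to Week 10) and footnote 6 (after Week 10), including End of Study. Measure direct bilirubin when total is above ULN, as Appendix 4 already provides.

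The cost is two footnote edits and at most 2 × 18 = 36 extra assay results per patient (not counting any direct bilirubin), with no new visit or procedure. More liver events may be reported, some of them due to liver metastases.

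A weaker alternative is to require both analytes whenever AST or ALT is at least 3 times ULN, whatever the baseline. That closes the second gap but not the first.
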